**5.2.1. Exclusion Criteria for Healthy Participants**

MEDICAL CONDITIONS
1. Any clinically significant concomitant disease or condition that could interfere with, or for which the treatment of might interfere with, the conduct of the study, or that would, in the opinion of the Investigator, pose an unacceptable risk to the participant in this study
2. A current diagnosis of migraine headache
3. Positive Hepatitis A virus antibody (HAV Ab (IgM), or positive for HBV, hepatitis C virus (HCV) or human immunodeficiency virus (HIV) at screening
4. ALT $> 1$ x ULN
5. Bilirubin $> 1.5$ x ULN (isolated bilirubin $> 1.5$ x ULN is acceptable if bilirubin is fractionated and direct bilirubin $< 35\%$ )
6. Current or chronic history of liver disease, or known hepatic or biliary abnormalities (except for Gilbert's syndrome or asymptomatic gallstones)
7. Corrected QT interval (QTc) $> 450$ msec
NOTE: The QTc is the QT interval corrected for heart rate according to Bazett's formula (QTcB), Fridericia's formula (QTcF), and/or another method, machine-read or manually over-read. The specific formula that will be used to determine eligibility and discontinuation for an individual subject should be determined prior to initiation of the study. In other words, several different formulae cannot be used to calculate the QTc for an

MEDICAL CONDITIONS

individual subject and then the lowest QTc value used to include or discontinue the subject from the trial.
 
For purposes of data analysis, QTcB, QTcF, another QT correction formula, or a composite of available values of QTc will be used as specified in the Reporting and Analysis Plan (RAP).
 
8. Medical history of cardiac arrhythmias or cardiac disease or a family or personal history of long QT syndrome. Any significant arrhythmia which, in the opinion of the Investigator or GSK Medical monitor (if required), will interfere with the safety for the individual participant.
 
9. Evidence of previous myocardial infarction (does not include ST segment changes associated with re-polarization).
 
10. Signs and symptoms suggestive of COVID-19. NOTE: Assessments will be performed in accordance with local site procedure.
 
11. For participants in Part 2A only:
 
 
i. Personal history or family history of peripheral neuropathy
 
ii. A score <math>\geq 4</math> on the Toronto Clinical Scoring System for Polyneuropathy
 

PRIOR/CONCOMITANT THERAPY AND CLINICAL STUDY EXPERIENCE

12. Past or intended use of over-the-counter or prescription medication, including vitamins, herbal and dietary supplements (including St John's Wort) within 7 days before the first dose of study intervention, unless in the opinion of the Investigator, the medication will not interfere with the study procedures or compromise participant safety.
 
NOTE: Use of paracetamol or acetaminophen, at doses <math>\leq 2</math> g/day and/or use of simple analgesics is acceptable
 
13. Recent donation of blood or blood products such that participation in the study would result in loss of blood in excess of 500 mL within 56 days
 
14. The participant has participated in a clinical trial and has received an investigational product within the following time period prior to the first dosing day in the current study: 30 days, 5 half-lives or twice the duration of the biological effect of the investigational product (whichever is longer)
 
15. Exposure to more than 4 investigational medicinal products within 12 months prior to the first dosing day
 
16. Unwillingness or inability to follow the procedures outlined in the protocol or any other type of medical research within 30 days of randomization

**DIAGNOSTIC ASSESSMENTS**

- 17. Positive pre-study drug/alcohol screen
- 18. Positive test for COVID-19 infection

**NOTE:** Assessments will be performed in accordance with local site procedure

**OTHER EXCLUSIONS**

- 19. Current or history of drug abuse
- 20. Regular alcohol consumption within 6 months prior to the study defined as:  
  
An average weekly intake of > 14 units for both males and females; one unit is equivalent to 8 g of alcohol: a half-pint (~240 mL) of beer, 1 glass (125 mL) of wine or 1 (25 mL) measure of spirits
- 21. Current or previous use of tobacco- or nicotine-containing products (e.g., cigarettes, nicotine patches or electronic devices) within 6 months before screening and/or have a smoking pack history of > 5 pack years  
  
**NOTE:** 1 pack year = 20 cigarettes per day for 1 year or 5 cigarettes per day for 4 years
- 22. Positive breath carbon monoxide test indicative of recent smoking at screening or each in-house admission to the clinical research unit
- 23. Sensitivity to any of the study interventions, or components thereof, or drug or other allergy that, in the opinion of the investigator, contraindicates participation in the study

**5.2.2. Exclusion Criteria for PLWCHB****MEDICAL CONDITIONS**

- 24. Clinically significant abnormalities affecting physical or mental health in medical history or on physical examination (e.g., moderate-severe liver disease other than chronic HBV, acute coronary syndrome within 6 months of screening, major surgery within 3 months of screening, significant/unstable cardiac disease (including pacemaker or AICD), uncontrolled diabetes, bleeding diathesis or coagulopathy), apart from chronic HBV infection.
- 25. Co-infection with:
  - a. Current or past history of HCV
  - b. HIV
  - c. Hepatitis D virus (HDV)

26. History of or suspected liver cirrhosis and/or evidence of cirrhosis as determined by:
- a. both aspartate aminotransferase (AST)-Platelet Index (APRI) >2 and FibroSure/FibroTest result >0.7
  - b. Regardless of APRI or FibroSure/FibroTest score, if the participant meets 1 of the following criteria, they will be excluded from the study
    - i. Liver biopsy-based diagnosis of cirrhosis (e.g. Metavir Fibrosis Grade F4)
    - ii. Liver stiffness >12 kPa
27. Diagnosed or suspected hepatocellular carcinoma as evidenced by the following:
- a. Alpha-fetoprotein concentration  $\geq 200$  ng/mL
  - b. If the screening alpha-fetoprotein concentration is  $\geq 50$  ng/mL and <200 ng/mL, the absence of liver mass must be documented by imaging within 6 months before randomization
28. History of malignancy within the past 5 years with the exception of specific cancers that are cured by surgical resection (e.g., skin cancer). Participants under evaluation for possible malignancy are not eligible
29. History of vasculitis or presence of symptoms and signs of potential vasculitis [e.g., vasculitic rash, skin ulceration, repeated blood detected in urine without identified cause] or history/presence of other diseases that may be associated with vasculitis condition (e.g., systemic lupus erythematosus, rheumatoid arthritis, relapsing polychondritis, mononeuritis multiplex)
30. History of extrahepatic disorders possibly related to HBV immune conditions (e.g., nephrotic syndrome, any type of glomerulonephritis, polyarteritis nodosa, cryoglobulinaemia, uncontrolled hypertension)
31. History of alcohol or drug abuse/dependence
- a. Current alcohol use as judged by investigator to potentially interfere with participant compliance
  - b. History of or current drug abuse/dependence as judged by the investigator to potentially interfere with participant compliance
- NOTE:** Refers to illicit drugs and substances with abuse potential. Medications that are used by the participant as directed, whether over-the-counter or through prescription, are acceptable and would not meet the exclusion criteria
32. History of or other evidence of bleeding from esophageal varices
33. Documented history or other evidence of metabolic liver disease within 1 year of randomization
34. Documented history or other evidence of diabetes (regardless of insulin-dependence)

**MEDICAL CONDITIONS**

35. Personal history or family history of peripheral neuropathy
36. A score >4 on the Toronto Clinical Scoring System for Polyneuropathy
37. History of having received or currently receiving any systemic anti-neoplastic (including radiation) or immune-modulatory treatment (including systemic oral corticosteroids) within the 3 months prior to randomization or the expectation that such treatment will be needed at any time during the study
38. Currently taking, or has taken within 12 months of randomization, any interferon-containing therapy.
39. Abnormal and clinically significant 12-lead ECG finding. The investigator will determine the clinical significance of each abnormal ECG finding in relation to the participant's medical history and exclude participants who would be at undue risk by participating in the study. An abnormal and clinically significant finding that would preclude a participant from entering the study is defined as a 12-lead tracing that is interpreted as, but not limited to, any of the following:
  - a. Atrial fibrillation (AF) with rapid ventricular rate >120 bpm
  - b. sustained or non-sustained ventricular tachycardia
  - c. second degree heart block Mobitz type II and third-degree heart block
  - d. QTcF >450 msec

**PRIOR/CONCOMITANT THERAPY AND CLINICAL STUDY EXPERIENCE**

40. Currently taking, or taken within 3 months prior to randomisation, any immunosuppressing drugs (e.g., prednisone), other than a short course of therapy ( $\leq 2$  weeks) or topical/inhaled steroid use
41. Participants for whom immunosuppressive treatment is not advised, including therapeutic doses of steroids, will be excluded
42. Participants requiring anti-coagulation therapies (for example warfarin, Factor Xa inhibitors or anti-platelet agents like clopidogrel or aspirin)
43. The participant has participated in a clinical trial and has received an investigational product within the following time period prior to the first dosing day in the current study: 5 half-lives (if known) or twice the duration (if known) of the biological effect of the study treatment (whichever is longer) or 90 days (if half-life or duration is unknown)
44. Prior treatment with any oligonucleotide or small interfering RNA (siRNA) within 12 months prior to the first dosing day. Patients who have received a course of bepirovirsen, even if it has been more than 12 months, are excluded.

**DIAGNOSTIC ASSESSMENTS**

45. Positive test for COVID-19 infection

**NOTE:** Testing must be performed. Method of testing will be in accordance with local site procedure.

## 46. Laboratory results as follows:

- a. Serum albumin  $\leq 3.5$  g/dL
- b. Glomerular filtration rate (GFR)  $\leq 60$  mL/min /1.73m^2 as calculated by the chronic kidney diseases epidemiology collaboration (2021 CKD-EPI) formula
- c. INR  $> 1.25$
- d. Platelet count  $< 140 \times 10^9$  /L
- e. Total bilirubin  $> 1.25 \times$  ULN
- f. Urine ACR  $\geq 0.03$  mg/mg (or  $\geq 30$  mg/g). In the event of an ACR above this threshold, eligibility may be confirmed by a second measurement.

**NOTE:** In cases where participants have low urine albumin and low urine creatinine levels resulting in a urine ACR calculation  $\geq 0.03$  mg/mg, the investigator should confirm that the participant does not have a history of diabetes, hypertension or other risk factors that may affect renal function.

**OTHER EXCLUSIONS**

## 47. Regular alcohol consumption within 6 months prior to the study defined as:

An average weekly intake of  $> 14$  units for both males and females; one unit is equivalent to 8 g of alcohol: a half-pint (~240 mL) of beer, 1 glass (125 mL) of wine or 1 (25 mL) measure of spirits

## 48. Sensitivity to any of the study interventions, or components thereof, or drug or other allergy that, in the opinion of the investigator, contraindicates participation in the study

## 49. Participants with a fear of needles

**5.3. Lifestyle Considerations****5.3.1. Meals and Dietary Restrictions**

- Refrain from consumption of red wine, Seville oranges, grapefruit or grapefruit juice, pomelos, exotic citrus fruits, or grapefruit hybrids from 7 days before the start of GSK3965193 treatment until after the final dose.

CCI

**5.3.2. Caffeine, Alcohol, and Tobacco****Inpatient**

Parts 1 and 2 only: During each dosing session, participants will abstain from ingesting caffeine- or xanthine-containing products (e.g., coffee, tea, cola drinks, and chocolate) for 24 hours before the start of dosing until after collection of the final PK and/or

pharmacodynamic sample. Other decaffeinated drinks will be permitted except during fasting periods where these are required in Part 2.

Alcohol consumption and use of tobacco products are not permitted in the clinical unit.

### **Outpatient**

During each visit, participants will abstain from alcohol for 24 hours before the start of dosing until after collection of the final PK and/or pharmacodynamic sample.

Participants who use tobacco products will be instructed that use of nicotine-containing products (including nicotine patches and other delivery devices such as vaporizers) will not be permitted while they are in the clinical unit.

### **5.3.3. Activity**

Participants will abstain from strenuous exercise for 72 hours before each blood collection for clinical laboratory tests. For the duration of the study, until final follow-up, participants are encouraged to refrain from changing their activity beyond that which they normally perform. Additionally, participants will abstain from taking creatine-containing exercise supplements for all parts of the study.

### **5.4. Screen Failures**

Screen failures are defined as participants who consent to participate in the clinical study but are not subsequently randomized. A minimal set of screen failure information is required to ensure transparent reporting of screen failure participants to meet the Consolidated Standards of Reporting Trials (CONSORT) publishing requirements and to respond to queries from regulatory authorities. Minimal information includes demography, screen failure details, eligibility criteria, any protocol deviations and any serious adverse events (SAEs).

Individuals who do not meet the criteria for participation in this study (screen failure) may be rescreened once. Individuals who fall out of the screening window, may be rescreened at the discretion of the investigator and site. Individuals who do not meet the criteria for participation only due to COVID-19 infections may also be rescreened after recovery. Rescreened participants should be assigned a new participant identifier for every screening/rescreening event. Previously assigned participant identifier(s) are to be recorded in participants' eCRF.

### **5.5. Criteria for Temporarily Delaying Administration of Study Intervention**

Not Applicable.

## 6. STUDY INTERVENTIONS AND CONCOMITANT THERAPY

Study intervention is defined as any investigational product(s), marketed product(s), placebo, or medical device(s) intended to be administered to a study participant according to the study protocol. An investigational product is defined as pharmaceutical form of an active substance. A placebo is defined as an inactive substance that looks the same as, and is given in the same way as, the investigational product being studied. No non-GSK comparators are used in this study. CCI

[REDACTED]

[REDACTED]

[REDACTED]

### 6.1. Study Intervention(s) Administered

The following products will be received by the participant as per the protocol design.

Parts 1 and 2A - CCI

[REDACTED]

Part 2B - CCI

[REDACTED]

Part 3 - CCI

[REDACTED]

Part 4 - CCI

[REDACTED]

CCI

[REDACTED]

CCI

The site of injection of bepirovirsen will be recorded for each participant and dose(s). Sites of injection are listed in order of preference and are a guide for the clinical staff.

CCI

Injections should be rotated within each anatomical site or site(s) of injection should be changed administration-to-administration. Injection into areas with ongoing injection site reactions should be avoided.

## **6.2. Preparation/Handling/Storage/Accountability**

The investigator or designee must confirm appropriate temperature conditions have been maintained during transit for all study intervention received and any discrepancies are reported and resolved before use of the study intervention.

Only participants enrolled in the study may receive study intervention and only authorized site staff may supply or administer study intervention. All study interventions must be stored in a secure, environmentally controlled, and monitored (manual or automated) area in accordance with the labeled storage conditions with access limited to the investigator and authorized site staff.

The investigator, institution, or the head of the medical institution (where applicable) is responsible for study intervention accountability, reconciliation, and record maintenance (i.e., receipt, reconciliation, and final disposition records).

Further guidance and information for the final disposition of unused study intervention are provided in the Pharmacy Manual.

Under normal conditions of handling and administration, study intervention is not expected to pose significant safety risks to site staff. Take adequate precautions to avoid direct eye or skin contact and the generation of aerosols or mists. In the case of unintentional occupational exposure notify the study monitor, Medical Monitor and/or GSK study contact.

A Material Safety Data Sheet (MSDS)/equivalent document describing occupational hazards and recommended handling precautions either will be provided to the investigator, where this is required by local laws, or is available upon request from GSK.

## **6.3. Measures to Minimize Bias: Randomization and Blinding**

All participants will be centrally randomized using a Randomisation and Trial Supply Management System (RTMS). Before the study is initiated, the log in information and directions for the RTMS will be provided to each site.

Study intervention will be dispensed at the study visits summarized in the SoA. Returned study intervention should not be re-dispensed to the participants.

On Day 1 of the first dosing for each cohort, participants will be assigned a unique randomisation number in ascending numerical order. The randomisation number encodes the participant's assignment to either GSK3965193 or placebo, according to the randomisation schedules generated prior to the study by the Statistics Department at GSK, using validated internal software. The Principal Investigator (PI) or delegated responsible person will assign the randomisation numbers as described above and the randomisation number will be entered in the case report form (CRF). In Part 4, all participants will receive bepirovirsen in addition to the randomised treatment.

This study (Parts 1, 2A, 3 and 4) is double blind with participants and the site staff blinded to each participant's assigned study intervention throughout the course of the study. In order to maintain this blind, in Parts 1 and 2 an unblinded pharmacist will be responsible for the reconstitution and dispensing of all study intervention; in Parts 3 and 4 all site staff will be blinded. Once a treatment period in Part 1 or a cohort in Part 2A has completed, selected members of the sponsor staff were unblinded to the treatment allocations of participants who completed the treatment to enable the analysis and modelling of PK data to start the next period or cohort. The GSK/clinical research organization personnel did not have access to participant-specific treatment assignment to avoid potentially introducing bias in discussion with the study site. In Part 1 and Part 2A, the pharmacokineticists, statisticians and programmers, however, needed access to participant randomization during the course of the single dose escalation and repeat dose escalation parts of the study for analysis purposes to support dose adjustments and escalations. Other GSK staff may be included in discussions around dose adjustments and progression if it is deemed necessary and relevant by the above-mentioned GSK study team members. Part 2B is open label. The Sponsor will present data at Dose Escalation Committee (DEC) and Safety Review Team (SRT) meetings in a blinded fashion when interacting with site staff.

Treatment sensitive lab data have been identified and include PK data, exploratory HBV biomarker data and in-stream HBsAg and HBV DNA results. CCI [REDACTED]

The blind may be broken if, in the opinion of the Investigator, it is in the participant's best interest for the investigator to know the study treatment assignment. The Sponsor study team must be notified before the blind is broken unless identification of the study treatment is required for a medical emergency in which the knowledge of the specific blinded study treatment will affect the immediate management of the participant's condition. In this case, the Sponsor study team must be notified within 24 hours after breaking the blind. The date and reason that the blind was broken must be recorded in the source documentation and electronic case report form (eCRF), as applicable.

A participant will be withdrawn if the participant's intervention code is unblinded by the investigator or treating physician. The primary reason for discontinuation (the event or condition which led to the unblinding) will be recorded in the CRF.

GSK's Global Clinical Safety and Pharmacovigilance (GCSP) staff may unblind the intervention assignment for any participant with an SAE. If the SAE requires that an expedited regulatory report be sent to one or more regulatory agencies, a copy of the report, identifying the participant's intervention assignment, may be sent to investigators in accordance with local regulations and/or GSK policy.

GSK staff analysing samples derived from this study will be unblinded. Drug concentration information that may unblind the study will only be shared with the DMPK Study Director and scientists who are conducting and reporting the GSK3965193 metabolism study which is separate from this protocol. This information is needed to differentiate active-dosed participants from placebo to inform on the metabolite

identification study conduct. Drug concentration information will not be reported to investigative sites or blinded personnel until the study has been unblinded.

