## 7. DISCONTINUATION OF STUDY INTERVENTION AND PARTICIPANT DISCONTINUATION/WITHDRAWAL

### 7.1. Discontinuation of Study Treatment

In rare instances, it may be necessary for a participant to permanently discontinue study treatment. A participant may discontinue study treatment at any time at his/her own request. Additionally, study treatment may be withdrawn at any time at the discretion of the Investigator for safety, behavioural or administrative reasons.

If study treatment is permanently discontinued, the participant will remain in the study to be evaluated for safety and efficacy assessments. If a participant discontinues study treatment, an early discontinuation (ED) visit should be performed. See the SoA for data to be collected at the time of discontinuation of study treatment.

Following the ED visit the participant will enter the follow-up/post-treatment period following the visit schedule and required assessments that need to be completed, per the SoA.

In Part 3 of the study participants who discontinue study treatment during the GSK3965193 (or placebo) monotherapy phase should complete an ED visit and enter the two-week CCI follow-up/washout period. If the participant CCI and consented to optional bepirovirsen, progression into the optional bepirovirsen treatment period must not occur unless this has been discussed and agreed with the Medical Monitor prior to the day 43 visit.

If the patient withdraws consent to participate in the study completely the procedure described in Section 7.2 should be followed.

Stopping criteria, including their evaluation and confirmation, are detailed in Section 7.1.1 to Section 7.1.7. Participants meeting these criteria should be monitored until laboratory abnormalities resolve, stabilize, or return to within baseline values as indicated. This may be done at follow-up visits specified in the SoA or require additional visits to be scheduled.

Study treatment may be discontinued, and the participant potentially withdrawn from the study, if:

- A participant experiences a serious or severe clinically significant AE that in the clinical judgement of the Investigator, is possibly, probably or definitely related to investigational product.
- The participant initiates treatment with any prohibited medications.
- Individual or study level stopping criteria are met
- Deviation(s) from the protocol
- Withdrawal of consent by participant (or proxy)
- Discretion of the Investigator

- Participant is lost to follow-up

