### 7.1.2. QTc Stopping Criteria

If a clinically significant finding is identified including, but not limited to changes from baseline in QTcF after enrolment, the investigator or qualified designee will determine if the participant can continue in the study and if any change in participant management is needed. This review of the ECG printed at the time of collection must be documented. Any new clinically relevant finding should be reported as an AE.

The QTcF correction formula must be used for each participant to determine eligibility for and discontinuation from the study. This formula may not be changed or substituted once the participant has been enrolled. If an ECG demonstrates a prolonged QT interval, two more ECGs should be obtained over 5-10 mins and the average QTcF value of the three ECGs should be used to determine if the participant meets the QTc stopping criteria below.

A participant who meets the below QTc stopping criteria (based on the average of triplicate ECG readings) will be withdrawn from study intervention:

- QTcF >500 msec OR uncorrected QT >600 msec
- Change from baseline QTcF >60 msec

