## **7.2. Participant Discontinuation/Withdrawal from the Study**

- A participant may withdraw from the study at any time at his/her own request or may be withdrawn at any time at the discretion of the investigator for safety, behavioural, or compliance reasons. This is expected to be uncommon.
- At the time of discontinuing from the study, if possible, an early discontinuation visit should be conducted, as shown in the SoA. See SoA for data to be collected at the time of study discontinuation and follow-up and for any further evaluations that need to be completed.
- The participant will be permanently discontinued both from the study intervention and from the study at that time.
- If the participant withdraws consent for disclosure of future information, the sponsor may retain and continue to use any data collected before such a withdrawal of consent.
- If a participant withdraws from the study, he/she may request destruction of any samples taken and not tested, and the investigator must document this in the site study records.

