### **8.2.3. Electrocardiograms**

#### **8.2.3.1. 12-Lead Safety ECGs**

- Safety ECGs will be performed in semi-supine position after at least 5 minutes rest and printed and interpreted on-site by the Investigator to ensure participant safety.
- Triplicate OR Single 12-lead ECG will be obtained as outlined in the SoA (see Section 1.3) using an ECG machine that automatically calculates the heart rate and measures PR, QRS, QT, and QTc intervals. Refer to Section 7.1.2 for QTc withdrawal criteria and additional QTc readings that may be necessary.
- At each time point at which triplicate ECG are required, the ECGs will be obtained at least 2 minutes apart and over a recording period of up to 10 minutes.
- Baseline QTcF will be based on the average of 3 pre-dose ECGs collected on Day 1 (in Part 1, Day 1 pre-dose for each treatment period should be considered as baseline).
- Refer to Section 7.1.2 for QTc specific stopping criteria.

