### 8.3.5. Pregnancy

- Details of all pregnancies in female participants and female partners of male participants will be collected after the start of study intervention and until completion of the final follow up visit.
- If a pregnancy is reported, the investigator will record pregnancy information on the appropriate form and submit it to GSK within 24 hours of learning of the female participant pregnancy. While pregnancy itself is not considered to be an AE or SAE, any pregnancy complication or elective termination of a pregnancy for medical reasons will be reported as an AE or SAE.
- Abnormal pregnancy outcomes (e.g., spontaneous abortion, fetal death, stillbirth, congenital anomalies, ectopic pregnancy) are considered SAEs and will be reported as such.

- Any termination of pregnancy will be reported, regardless of fetal status (presence or absence of anomalies) or indication for procedure.
- The participant/pregnant female partner will be followed to determine the outcome of the pregnancy. The investigator will collect follow-up information on the participant/pregnant female partner and the neonate and the information will be forwarded to the sponsor.
- Any post-study pregnancy-related SAE considered reasonably related to the study intervention by the investigator will be reported to the sponsor as described in Section 10.3 (Appendix 3). While the investigator is not obligated to actively seek this information in former study participants, he or she may learn of an SAE through spontaneous reporting.
- Any female participant who becomes pregnant while participating in the study will discontinue study intervention or be withdrawn from the study.

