6.1.1. Participant Disposition

A summary of the number and percentage of participants who completed the study as well as those who prematurely withdrew from the study will be provided. Reasons for study withdrawal will be summarized. For those who have neither completed nor withdrawn, they will be categorized as on study intervention or in follow up.

A summary of study intervention status will be provided. This display will show the number and percentage of participants who have completed the scheduled study intervention, are ongoing with study intervention, or have discontinued study intervention prematurely, as well as primary reasons for discontinuation of study intervention.

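### Protocol 6.3 orders withdrawal after a code break without saying whether from study treatment or from the study, so a site could end follow-up that 7.1 would keep

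*Protocol*

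**What the plan says.** Protocol 6.3 lets the investigator break the blind when that is judged to be in the participant's best interest. The sponsor study team must be told beforehand or, in a medical emergency, within 24 hours afterwards. The section then sets a mandatory consequence: "A participant will be withdrawn if the participant's intervention code is unblinded by the investigator or treating physician." The sentence that follows asks for the main reason for discontinuation to be recorded in the CRF, again without saying discontinuation of what.

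Two later sections give different procedures. Protocol 7.1, on stopping treatment, says: "If study treatment is permanently discontinued, the participant will remain in the study to be evaluated for safety and efficacy assessments." An early discontinuation visit comes first, then the follow-up schedule. Protocol 7.2, on leaving the study, says: "The participant will be permanently discontinued both from the study intervention and from the study at that time."

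**The concern.** The rule is mandatory, and its missing object decides whether follow-up continues. Under 7.1 the participant stays and is measured. Under 7.2 participation ends.

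Code breaks of this kind are made for clinical reasons, so the participants affected are ones whose later course matters. If they leave the study, the data lost are unlikely to be missing at random. Two parts of the plan rely on such data:

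- **Safety.** Protocol Table 1 handles stopping GSK3965193 by treatment policy in Parts 2, 3 and 4, which uses data collected after dosing stops. Events already open are followed to resolution (8.3.3), but 8.3.1 does not oblige investigators to look for new events once participation has ended.
- **Part 4 complete response.** This primary endpoint requires HBsAg and HBV DNA results for six months after the planned end of bepirovirsen (8.1, Table 2). Table 2 handles stopping GSK3965193 by treatment policy, except where a wide disruptive event caused it. A study exit makes those results missing.

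**Working it through.** The point concerns wording, so no arithmetic applies. The check sets the relevant passages side by side.

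1. **Does 6.3 or its context supply the object?** No. Neither the rule nor the next sentence names one. The reference there to discontinuation does not help, because 7.2 uses the same word for leaving the study.

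2. **Does the list of reasons in 7.1 cover it?** No. Unblinding is not listed, and the lead-in is permissive: "Study treatment may be discontinued, and the participant potentially withdrawn from the study, if". Section 6.3 is mandatory. The lead-in also shows that remaining in the study is a default under 7.1, with exceptions.

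3. **How is withdrawal used elsewhere?** Both ways.
   - Treatment only: 8.2.3.1 says "Refer to Section 7.1.2 for QTc withdrawal criteria and additional QTc readings that may be necessary", yet under 7.1.2 the participant "will be withdrawn from study intervention". Withdrawal there means stopping treatment.
   - Study exit: 7.2 is the section whose title refers to withdrawal from the study. The risk table in 2.3.1 says that a participant who becomes pregnant leaves the study. SAP 6.1.1 (Part 3) links the word to the study ("Reasons for study withdrawal will be summarized") and reports discontinuation of study intervention in a separate display.
   - As alternatives: under 8.3.5 a participant who becomes pregnant "will discontinue study intervention or be withdrawn from the study". The protocol therefore treats the two as different outcomes.

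4. **What happens after the last blinded dose?** Section 6.3 keeps the blind throughout the study. In Part 4, GSK3965193/placebo and bepirovirsen are given together for 28 days, and bepirovirsen then continues (4.2.4). After that point there is no blinded product left to stop. The rule could then mean open-label bepirovirsen, the study, or nothing, and 6.3 does not say which.

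5. **Which analyses depend on the reading?**

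| Output | Effect of a study exit |
|---|---|
| Part 3 primary HBsAg estimand (SAP 1.1.1) | Little: while on-treatment, so data are cut at discontinuation on either reading |
| Part 3 GSK3965193/placebo treatment-emergent AEs (SAP 4.2.2.1) | Little: the window closes 7 days after the last dose |
| Part 3 supplementary estimand (SAP 1.1.3) | Possible, but run only if 4 or more participants have an intercurrent event |
| Part 3 bepirovirsen treatment-emergent AEs (SAP 4.3.1.2.3) | Possible: the window has no end date |
| Part 4 safety and complete response (Tables 1 and 2) | Direct: post-discontinuation data are needed |

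Parts 1 and 2 are complete and are not affected by a change now.

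**The case against.** The best reply is that the protocol already limits the damage. Four parts of it stand.

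- **The sponsor is told.** Because 6.3 requires notice of each code break before it happens or within 24 hours, a site need not interpret the rule alone and a wrong exit is unlikely to pass unnoticed. This lowers the risk but leaves the text unsettled.
- **7.2 does not shut off all data.** It asks for an early discontinuation visit where possible and refers to the schedule of activities for follow-up and further evaluations. That schedule is redacted, so how much follow-up would survive cannot be seen.
- **Bepirovirsen in Part 3 is partly covered.** Under 7.1, a participant who stops during the blinded monotherapy phase may go on to optional bepirovirsen only if the Medical Monitor agrees before the Day 43 visit. On the treatment-only reading this answers the question while blinded dosing is under way. No equivalent text is visible for Part 4 or for a later code break.
- **The treatment-only reading is plausible.** The QTc wording supports it, and a site that adopts it loses no follow-up.

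A reader might go further and infer that 6.3 requires study exit, or that follow-up would certainly be lost for good. The documents do not support either: 6.3 is silent on the object, and the surviving follow-up depends on redacted text. A reader might also infer a large effect from the long stretch of study time after the last blinded dose. Calendar time is not a count of code breaks, which are less likely once blinded dosing has ended. The stretch also differs with whether a Part 3 participant opts for bepirovirsen, and the Part 4 bepirovirsen duration is redacted.

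**Conclusion.** The concern holds as an ambiguity in a mandatory rule. On a natural reading, supported by the title of 7.2 and by SAP 6.1.1, a site following 6.3 could take a participant out of the study after a code break. That departs from the 7.1 default and may end scheduled safety, HBsAg and HBV DNA follow-up for clinically related reasons. The exposure lies mainly in safety follow-up and Part 4 complete response; the planned Part 3 GSK3965193 outputs are little affected.

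The effect cannot be sized. The number of code breaks is unknown and may be zero, the schedule of activities and the Part 4 analysis text are redacted, and the supplied SAPs cover Parts 1 to 3 only, so the handling of missing complete-response data in Part 4 is not visible. The conclusion assumes that no redacted passage defines the object. Confidence is medium. The correction should be made because it is cheap and the two readings lead to different data.

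**What to change.** Amend Protocol 6.3 to say that, after a code break by the investigator or treating physician:

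- GSK3965193/placebo is discontinued if it is still being given;
- the participant has the early discontinuation visit and then stays in the study for scheduled safety and efficacy assessments under 7.1, with later data flagged as unblinded, unless consent is withdrawn;
- the code break alone does not end study participation;
- open-label bepirovirsen may or may not continue (state which, for Parts 3 and 4), in line with the existing Medical Monitor rule for Part 3 in 7.1.

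The cost is a few sentences in an amendment. Follow-up after stopping treatment is already provided for in 7.1. The downside is that some follow-up is collected unblinded, which the flag makes visible. HBsAg and HBV DNA are laboratory measures, so this should matter less for them than for reported adverse events.
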